## **6.2. Data Handling**

### **6.2.1. Premature Withdrawal and Missing Data**

Missing data will not be imputed unless specified otherwise.

#### Determination of Treatment Emergent Adverse Event with Presence of Missing Data

The determination of treatment-emergent AE among records with missing data on starting date or time will be based on the non-missing components of their starting date and time. An AE with partial start date/time will be considered treatment-emergent in the following conditions:

- The start date of the event is completely missing;
- The start year of the event is equal to or later than the year of first infusion with the rest of the start date and time missing;
- The start year and month of the event are equal to or later than the year and month of first infusion with the rest of the start date and time missing;
- The start date of the event is equal to or later than the date of first infusion with the start time missing;
- The start date and hour of the event are equal to or later than the date and hour of first infusion with the minute of start time missing.

Correspondingly, an AE with partial start date/time will be considered as a pre-treatment event in the following conditions:

- The start year of the event is earlier than the year of first infusion with the rest of the start date and time missing;
- The start year and month of the event are earlier than the year and month of first infusion with the rest of the start date and time missing;
- The start date of the event is earlier than the date of first infusion with the start time missing;
- The start date and hour of the event are earlier than the date and hour of first infusion with the minute of start time missing.

### Determination of Prior/Concomitant Medications or Non-Drug Therapies with Presence of Missing Data

The determination of whether a medication or non-drug therapy is considered prior or concomitant will be based on the end date of the medication/therapy. A medication/therapy with missing data on its end date will be considered concomitant in the following cases (otherwise it will be considered as a prior medication/therapy):

- The end date of the medication/therapy is completely missing;
- The end year of the medication/therapy is equal to or later than the year of first infusion with the rest of the end date missing;
- The end year and month of the medication/therapy are equal to or later than the month and year of first infusion with the end day missing.

For determination of pHLH conventional treatment history (prior pHLH conventional medication or non-drug therapy), similar rules will be applied by replacing end date as start date of the medication/non-drug therapy.

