### **6.4. Demographics and Background Characteristics**

Subject demographics including sex, birth date, race, and whether the subject has child-bearing potential will be collected in CRF. Information on HLH history including pHLH diagnosis, genetic test result (molecular diagnosis), NK-cell functional test result, family history, and conventional treatment received will be collected in details via CRF. Medical history including name of the medical condition or event, start and end date, and ongoing status will be collected in CRF. Medical history data will be coded using the latest updated English version of Medical Dictionary for Regulatory Activities (MedDRA).

Analysis on demographic data and background characteristics will be based on all treated subjects. Subjects' demographic and background characteristics will be summarized using descriptive statistics. And data listings will be provided. For conventional treatment record, pHLH conventional treatment history including medication and non-drug therapy will be

presented. Prior pHLH conventional medication will be tabulated by anatomical main group and therapeutic subgroup, and prior pHLH conventional non-drug therapy will be tabulated by therapy name. A medication/non-drug therapy will be considered pHLH conventional medication/non-drug therapy if the indication is conventional pHLH treatment (ongoing or discontinued at screening) as reflected in the CRF. A pHLH conventional medication/therapy will be considered treatment history if the start date is earlier than the date of first infusion. For records with its start date completely or partially missing, similar method as described in [Section 6.2.1 will be applied \(replacing end date by start date in the specified rules\)](#). For medical history data, concurrent disease and condition will be tabulated separately from medical history record and historic event. A medical history record with its ongoing status specified as yes will be considered concurrent (and otherwise historic event). Medical history and concurrent disease will be tabulated at subject level grouping by System Organ Classes (SOCs) and Preferred Terms (PTs).

Analysis of safety assessments at screening visit will be based on all treated subjects, for other details please refer to [Section 6.10](#).

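### Conventional pHLH therapies whose start date is missing, or is partial and ties with first infusion, are left out of the treatment-history table because a default written for end dates is reused for start dates

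*SAP*

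**What the plan says.** SAP 6.2.1 first deals with prior and concomitant medication in general, where the split rests on the end date. With an incomplete end date, a record is concomitant in three cases. The first reads "The end date of the medication/therapy is completely missing". In the second, only a year is recorded, and it ties with or follows the first-infusion year. In the third, year and month are recorded without a day, and together they tie with or follow those of first infusion. For anything else, "otherwise it will be considered as a prior medication/therapy".

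The same section then extends this to conventional pHLH treatment history: "similar rules will be applied by replacing end date as start date of the medication/non-drug therapy". SAP 6.4 repeats the instruction as "replacing end date by start date in the specified rules". Neither place changes the default.

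SAP 6.4 also gives two tests for the history table. One identifies a record as conventional pHLH therapy, and is met when "the indication is conventional pHLH treatment (ongoing or discontinued at screening) as reflected in the CRF". The other concerns timing and is worded as follows: "A pHLH conventional medication/therapy will be considered treatment history if the start date is earlier than the date of first infusion".

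**The concern.** Assuming that an undated medication continued past first infusion is the cautious choice when the aim is to capture everything given alongside study drug. With start dates the aim is the opposite: to capture what was given before study drug. Keeping the same default means assuming that an undated therapy began on or after first infusion, and so removing it from the history.

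This conflicts with other information on the same record. The CRF indication describes treatment that was still running, or had been stopped, at screening, and Protocol 6.5.1.2 places screening in the 2 weeks before the first dose. An end date before first infusion, where there is one, also proves an earlier start, yet the swapped rule does not look at it.

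The trial enrols treatment-experienced patients, so the history table is where a reader sees what they had already received. SAP 6.13 summarises HLH history for publication before the final analysis, so a shortfall could be published first. Incomplete dates are foreseeable: Protocol 6.4.5 asks for all conventional pHLH treatment whenever it was given, and Protocol 6.5.2 accepts HLH history as far as it is available.

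**Working it through.** The plan states no figure to reproduce. The check applies the three rules literally, with start date in place of end date, and then asks how often a therapy that truly began before first infusion would be lost.

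**Step 1. Classification by date pattern**

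| Start date on record | Result of the swapped rule |
|---|---|
| Completely missing | Not history |
| Year only, same year as first infusion | Not history |
| Year only, earlier year | History |
| Year and month, same month as first infusion | Not history |
| Year and month, earlier month or year | History |
| Complete, before first infusion | History |

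A partial date later than first infusion is also not history, which is correct. The errors are in the missing and tied rows.

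**Step 2. Share lost, given that the date is incomplete**

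Assumption: first-infusion dates are spread evenly over a 365-day year (or a 30-day month). The 8-week and 2-week intervals are illustrative. They echo the induction length, and the lower end of the 2-3 week point for judging response, in Protocol 4.1.

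- Start completely missing: 100%, by the rule itself.
- Year only, true start 8 weeks (56 days) earlier: the years tie unless first infusion falls in the first 56 days of the year. (365 − 56)/365 = 309/365 = 84.7%.
- Year and month, true start 14 days earlier: the months tie unless first infusion falls in the first 14 days of the month. (30 − 14)/30 = 53.3%. With actual month lengths, (365 − 12 × 14)/365 = 197/365 = 54.0%.

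**Step 3. How the loss changes with the interval** (calendar year of 365 days)

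| True start before first infusion | Year-only records lost | Year-month records lost |
|---|---|---|
| 7 days | 98.1% | 77.0% |
| 14 days | 96.2% | 54.0% |
| 30 days | 91.8% | 1.9% |
| 60 days | 83.6% | 0% |
| 90 days | 75.3% | 0% |
| 180 days | 50.7% | 0% |
| 365 days | 0% | 0% |

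The year-only tie is the wide gap. The year-month tie matters only for therapy begun within about a month of first infusion.

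**Step 4. Effect of one record**

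With 10 to 18 patients, one patient is 1/18 = 5.6% to 1/10 = 10.0% of the table. A lost record moves a row by that much if it is the patient's only entry in that row.

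**Step 5. Where the record ends up**

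Take a therapy with an unknown start and an end date before first infusion. SAP 6.6 classes it as prior in the general medication tables, because that split uses the end date. For the same reason it is not in the concomitant pHLH table, and under the swapped rule it is not in the pHLH history table. It is therefore in neither pHLH-specific table.

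**Step 6. With the rule turned round**

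If an incomplete start date is history unless its known parts fall after first infusion, the share of true pre-infusion starts lost is 0% in every pattern tested.

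**The case against.** Several points on the other side stand.

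- A reader might infer that every partial start date is dropped. The SAP does not say that: dates in an earlier year or month fall to the prior default and stay in the table.
- The percentages apply only to records already lacking date parts, at chosen intervals. Protocol 6.4.5 requires dates for each medication, and Protocol 7 and 9.2 describe edit checks and queries, so there may be few such records, or none.
- It is tempting to say that therapies from earlier hospitals will vanish, or that patients will look untreated. No document says where gaps will arise. The partial-date rule keeps older therapy and loses recent therapy. A patient would look untreated only if all of that patient's records were missing or tied.
- The records are not lost from the report. They remain in the listings, and the SAP 6.6 tables classify them by end date. No endpoint, analysis set or eligibility decision uses the history table.
- It is also tempting to say that the CRF indication settles the matter, so that any record carrying it is always history. The CRF is not among the documents, and SAP 6.4 applies a start-date test after the indication test. Since the indication defines every conventional pHLH record, such a rule would override even a complete start date after first infusion.

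One point does not stand. It can be argued that calling the rules similar leaves the programmer free to reverse the default. SAP 6.4 spells out a plain substitution, and a rule that works only if someone silently corrects it should be corrected in writing.

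**Conclusion.** The concern holds in a limited form. Followed as written, SAP 6.2.1 and 6.4 leave out of the treatment-history table any conventional pHLH therapy whose start date is completely missing, or is partial and ties with the year, or the year and month, of first infusion. They do so even when other fields on the record point to an earlier start. An end date before first infusion is proof of that; the CRF indication is strong evidence on its face.

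The Step 2 losses (100%, about 85% and about 53%) rest on evenly spread infusion dates and are conditional on an incomplete date. They do not forecast how much of the table will be missing, because the documents do not allow the number of affected records to be estimated.

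The consequence is confined to one descriptive table and to its use in the SAP 6.13 baseline summary. Nothing supports reading it as a threat to the safety or efficacy results. It is still worth correcting: this is a stated rule that gives a wrong answer, in a table that describes the defining feature of the population.

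**What to change.** Replace the substitution sentence in both SAP 6.2.1 and SAP 6.4 with:

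> A conventional pHLH medication or non-drug therapy with a missing or partial start date is treatment history unless the known parts of its start date place the start after the first infusion; if its end date is before the first infusion it is treatment history. Records with a complete start date are classified by that date.

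The last sentence preserves the existing start-date test in 6.4.

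The cost is one replacement sentence in two places and a small program change, with no new data collection. The remaining risk runs the other way: a therapy begun after first infusion, with a tied or missing start date, could be counted as history. The indication test in 6.4 limits this, and such records can be checked at the data review meeting. The change should be in place before the SAP 6.13 summary is produced; if that summary already exists, its history table should be checked for excluded records.

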#### **6.2.2. Derivation and Transformation on Data**

Besides the calculation for certain endpoints (as listed below), which are based on data collected via CRF, no derivation or transformation will be applied. Outliers will be reported to data management function as a data issue to be resolved or confirmed before database lock. No special data handling will be done.

For the derivation of the achievement of Overall Response, refer to [Section 6.8.2](#).

Age (in years) = (Date of informed consent/assent – birth date + 1)/365.25, rounding up to integer;

Time to first overall response (in days) = Date of the first achievement of response (Complete Response, Partial Response or HLH Improvement) – date of the first dose of emapalumab + 1, patients without a response will be censored at the date of EOT visit or last assessment;

Cumulative duration of response (in days) = Date of EOT visit – date of the first achievement of response + 1, for patients who achieve a response, lost that response, and then achieve any response subsequently, the total time in response will be calculated by adding together these separate periods in response;

Survival to start of HSCT conditioning (in days) = Date of death – date of first dose of emapalumab + 1, patients with no event will be censored at date of the start of conditioning for HSCT or last contact for patients who did not undergo HSCT;

Survival after HSCT (in days, calculated only for patients underwent HSCT) = Date of death – HSCT performed date+ 1, patients with no event will be censored at date of last contact;

Overall survival (in days) = Date of death – date of first dose of emapalumab + 1, patients with no event will be censored at date of last contact;

Dose administered (mg) = Prescribed dose [mg] × Approximate Proportion Administered [%];

Total duration of dosing (days) = Date of last infusion – date of first infusion + 1;

Average dosing frequency (times per day) = The total number of records of emapalumab infusion / total duration of dosing;

Prescribed dose change from first dosing (%) = (Prescribed dose at visit [mg] - prescribed dose at first dosing [mg]) / prescribed dose at first dosing [mg] × 100%.

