4.1 Background

Hemophagocytic lymphohistiocytosis (HLH) is a hyperinflammatory syndrome of pathologic immune activation. HLH comprises primary (genetic/familial) HLH and secondary HLH (sHLH), both clinically described by a dysregulation of the immune system leading to a profound hypercytokinemia with deleterious consequences on various tissues and organs [3].

Primary HLH (pHLH) is a heterogeneous recessive disorder characterized by a severe impairment or absence of cytotoxic function by natural killer (NK) and CD8+ T cells with striking activation of the immune system. While pHLH is mostly seen in infancy and early childhood with an estimated prevalence in Europe of 1/50,000 live births [4], adult cases are described [5-7]. The incidence of HLH in China has not been reported in literature. The disease is invariably fatal if untreated, with a median survival of less than 2 months after diagnosis [8, 9].

Typical features of HLH are [10]:

- Prolonged fever
- Splenomegaly and hepatomegaly
- Cytopenia
- Hyperferritinemia
- Hypertriglyceridemia
- Hypofibrinogenemia
- Lymphohistiocytic infiltrate
- Hypercytokinemia.

There is mounting evidence supporting the pivotal pathogenic role of interferon gamma (IFN γ) in the development of both primary [11, 12] and secondary forms of HLH [13-16].

Perforin knock-out mice represent a relevant model for pHLH since, once infected with lymphocytic choriomeningitis virus (LCMV), they develop an HLH-like disease dependent on CD8+ T cells and IFN γ production, with many of the clinical and laboratory features of the human disease. When the high circulating levels of IFN γ are neutralized by the administration of an anti-IFN γ antibody, not only are the clinical and laboratory abnormalities reverted, but also

survival rate is dramatically improved. On the contrary, the inhibition of many other cytokines had no impact on survival [11].

Further strengthening the importance of IFN γ in pHLH are the high concentrations of circulating IFN γ levels found in pHLH patients [3, 17, 18], with IFN γ levels above the upper limit of normal in all patients, and above 1000 pg/mL in 53.5% of the cases.

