6.2 Discussion of study design, including the choice of control groups

Open-label, single arm design of this prospective study is chosen, considering extreme rarity of the disease under study, its life-threatening nature, and lack of licensed alternative therapeutic approaches for the patients who have already received conventional HLH therapy without satisfactory response, or developed intolerance to it. For the same reasons, sample size is not driven by the statistical calculations, but rather by pragmatic considerations.

HLH is a challenging condition to manage, and disease control is known to be impacted by intercurrent conditions, such as infections. This is reflected in the flexible dosing schedule, which is the basis of the current established emapalumab dosing regimen for pHLH. Background treatment with dexamethasone with at least 5 mg/m²/day, or at the same dose administered prior to screening if higher, will be put in place. Additional HLH treatments (etoposide as a drug of choice) will be allowed, provided specific conditions, outlined in Section 6.4.5.2.3 are fulfilled.

It is expected that most patients with pHLH will proceed to HSCT whenever possible

Treatment duration, which is expected to last until start of conditioning for HSCT, has been defined based on previous experience and observed time required to proceed to HSCT; logistical considerations (e.g., donor unavailability) that may at times delay HSCT, were also considered. Treatment is thus allowed to be flexible but is not recommended to exceed 6 months.

Schedule of Assessments takes into consideration the limitations imposed by the expected young age of the patients, and a significant number of standard of care assessments and interventions that may be needed for HLH management. Windows are implemented to minimize the study burden.

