6.3.1 Inclusion criteria

A patient must fulfill the following criteria in order to be included in the study:

1. Male and female HLH patients of any age.
2. Patients diagnosed with confirmed or suspected pHLH, based on; a molecular diagnosis or familial history consistent with pHLH or fulfilment of HLH-2004 diagnostic criteria, i.e., five out of eight of the criteria below:

- Fever
 - Splenomegaly
 - Cytopenias affecting 2 of 3 lineages in the peripheral blood (hemoglobin <90 g/L; platelets <100 x 10⁹/L; neutrophils <1 x 10⁹/L)
 - Hypertriglyceridemia (fasting triglycerides ≥3 mmol/L or ≥265 mg/dL) and/or hypofibrinogenemia (≤1.5 g/L)
 - Hemophagocytosis in bone marrow, spleen, or lymph nodes, with no evidence of malignancy.
 - Low or absent NK-cell activity ⁱ
 - Ferritin ≥500 µg/L
 - Soluble CD25 (sCD25; i.e., soluble IL-2 receptor) ≥2400 U/mL ⁱⁱ
3. Presence of active HLH disease as assessed by the investigator.
 4. Patients must fulfil one of the following criteria as assessed by the investigator:
 - Having not responded to previous conventional treatment of HLH
 - Having not achieved a satisfactory response to previous conventional treatment of HLH or worsened
 - Having reactivated ⁱⁱⁱ
 - Showing intolerance to previous conventional treatment of HLH
- At the time of enrollment, eligible patients might still be receiving treatment (induction or maintenance) or might have already discontinued it.
5. Expectation of survival beyond 1 week as judged by the investigator.
 6. Patient has expectation of proceeding to HSCT
 7. Informed consent signed by the patient (as required by local law), or by the patient's legally authorized representative(s) with the assent of patients who are legally capable of providing it, as applicable.
 8. Willing to use highly effective methods of contraception from study drug initiation to 6 months after the last dose of study drug, if female and of childbearing potential.

In case of use of oral contraception women should have been stable on the same brand (or generic equivalent) for a minimum of 3 months before taking study treatment. Women are considered post-menopausal and not of childbearing potential if they have had 12 months of natural (spontaneous) amenorrhea with an appropriate clinical profile (e.g., age appropriate, history of vasomotor symptoms) or have had surgical bilateral oophorectomy (with or without hysterectomy) or tubal ligation at least six weeks ago.

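### The SAP rounds age up, so no infant can be reported as younger than 1 year and every patient appears at least one year above completed age

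*SAP*

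**What the plan says.** SAP section 6.2.2 gives the only age rule in either document. Age in years is (consent or assent date − "birth date + 1)/365.25, rounding up to integer". The same section says that nothing beyond its listed calculations will be derived or transformed. Neither document gives an age in months, a decimal age or an exception for infants.

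Birth date is the source: "Subject demographics including sex, birth date, race, and whether the subject has child-bearing potential will be collected in CRF" (SAP 6.4). Derived age then enters the demographic tables, since "Subjects' demographic and background characteristics will be summarized using descriptive statistics" (SAP 6.4). SAP 6.1 specifies mean, standard deviation, median, quartiles, minimum and maximum for continuous variables. SAP 6.13 adds a baseline summary, produced before the final analysis and intended for publication.

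On who will be enrolled, Protocol 6.3.1 admits "Male and female HLH patients of any age", Protocol 4.1 states that "pHLH is mostly seen in infancy and early childhood", and Protocol 6.2 refers to the "limitations imposed by the expected young age of the patients".

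**The concern.** The usual convention for age in whole years is completed years, which rounds down. This rule rounds up, and it also adds a day first. In an adult trial the error would be a small blemish. Here many patients may be under one or two years old, and a one-year error is then as large as the age itself.

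Two things are at stake. The published description of a group of only 10 to 18 patients would be wrong in its mean, median, quartiles, minimum and maximum. The age summary would also be unable to show that any infant was treated, because a 1-month-old and an 11-month-old would both appear as 1 year. Readers comparing this group with the global programme need that information.

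**Working it through.** **Inputs.** The formula and rounding rule are from SAP 6.2.2. Write *d* for the days from birth to consent. The plan's age is then ceil((*d* + 1)/365.25). The documents give no worked age to reproduce, so the rule was applied directly and compared with completed years.

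**Infants.** Since *d* is at least 0, (*d* + 1)/365.25 is at least 1/365.25 = 0.0027, and the ceiling is at least 1.

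| Age in days | (*d* + 1)/365.25 | Reported | Completed years |
|---|---|---|---|
| 0 | 1/365.25 = 0.0027 | 1 | 0 |
| 30 | 31/365.25 = 0.0849 | 1 | 0 |
| 184 | 185/365.25 = 0.5065 | 1 | 0 |
| 364 | 365/365.25 = 0.9993 | 1 | 0 |

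**Birthdays.**

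| Birthday | *d* | (*d* + 1)/365.25 | Reported |
|---|---|---|---|
| 1st | 365 | 366/365.25 = 1.0021 | 2 |
| 2nd | 730 | 731/365.25 = 2.0014 | 3 |
| 3rd | 1095 | 1096/365.25 = 3.0007 | 4 |
| 4th | 1461 | 1462/365.25 = 4.0027 | 5 |
| 5th | 1826 | 1827/365.25 = 5.0021 | 6 |
| 18th | 6574 | 6575/365.25 = 18.0014 | 19 |

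**Why every birthday tips over.** On the *k*-th birthday *d* = 365*k* + *L*, where *L* is the number of leap days passed. Over the dates that matter here, *L* is at least *k*/4 rounded down, so *L* + 1 always exceeds *k*/4. Hence *d* + 1 exceeds 365.25*k*, and the ceiling is at least *k* + 1. The same holds on every later day, so each patient is reported at least one year above completed age.

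**Exhaustive check.** All birth dates from 2000 to 2024 except 29 February were run.
- On birthdays 1 to 18, all 164,250 results were too high by exactly one year.
- Over every day of the first year of life (3,332,874 days), none gave 0. The result was 1 on 3,330,625 days and 2 on 2,249 (0.07%). The 2s fall just before a first birthday when a leap day intervenes. For example, birth on 1 March 2023 with consent on 29 February 2024 gives 366/365.25 = 1.0021, reported as 2.
- On a grid of births from 2005 to 2024 with consent dates to mid-2025, 99.92% of ages were one year above completed age and 0.08% were two years above.

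**Alternatives.**
- Rounding up without the extra day still overstates 59,956 of 164,250 birthdays (36.5%).
- Rounding the same formula to the nearest integer is right on the birthdays worked as examples, but reports 1 on 1,672,124 of the 3,332,874 infant days (50.2%), roughly the second half of the first year.
- Rounding the same formula down is right on all 164,250 birthdays and wrong (1 instead of 0) only on the 2,249 leap-day infant days.

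**Effect on the summary.** A shift of one year in nearly every patient raises the mean, median, quartiles, minimum and maximum by about one year relative to completed age and leaves the standard deviation almost unchanged. The minimum can never be below 1. Against exact decimal age the overstatement averages about half a year, if ages are spread evenly within each year. It reaches a full year on the day of birth and about 11 months at 30 days: (365.25 − 30)/365.25 = 0.92 year.

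**The case against.** The strongest counter-argument is that little depends on derived age. It enters no endpoint formula and no analysis set, SAP 6.11 plans no subgroups, and no hypothesis is tested. Study drug is dosed by weight, and the glucocorticoid calculation uses height and weight. Birth date is collected and all data are to be listed, so infants remain identifiable in the listings and age can be re-derived at any time. This stands, and it limits the consequence to description. It does not make the tabulated ages right.

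The phrase may also be loose English for ordinary rounding. The text does not say so, and SAP 6.1 describes its other rounding as rounding to a number of decimals, so a programmer would reasonably code a ceiling here. If rounding to nearest was meant, the line still needs correcting, and older infants would still be shown as 1.

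The table shells and dataset specifications (SAP 11) are separate documents and were not available. They may add age in months or age bands. That is possible, but the SAP's own rule would then disagree with them.

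Finally, any whole-year convention departs from exact age. Completed years understate it by about half a year on average, under the same assumption of even spread. This is a fair point about the half-year figure, and it is why completed years is the better yardstick. On that yardstick the rule is wrong by one year for essentially everyone. The two-year cut-off for reporting months, suggested below, is a reporting choice and does not come from the documents.

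**Conclusion.** The concern holds. As written, the rule cannot return an age below 1 and puts every patient at least one year above completed age: exactly one year in 99.92% of the grid, two years in the rare leap-day cases. This rests on reading the rule literally and on taking completed years as the standard.

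Safety and efficacy results are unaffected, and the error is recoverable from birth date. It should still be corrected before any baseline table is run. The age row would be wrong for every patient in a small, mostly young group, and the baseline summary may be published ahead of the final analysis.

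**What to change.** In SAP 6.2.2, define age as completed years at consent or assent, computed from calendar dates: year of consent minus year of birth, less one if that year's birthday has not yet been reached. This drops the extra day, the 365.25 divisor and the upward rounding, and it removes the leap-day remainder that rounding the current formula down would leave.

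Completed years alone would show all infants as 0. Add age in months to one decimal for patients under 2 years, and summarise it beside age in years. Carry the same rule into the dataset specification and table shells so that the three documents agree.

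The cost is one derivation line, plus one further line for months. No new data are needed.
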